Outcome Measures	Electronic, web-based randomisation. Assessors blinded but participants cannot be blinded.		
Statistical Methods	Feasibility of randomised trial including patient feasibility, outcomes feasibility and site and clinician feasibility		

ABBREVIATIONS

- AE Adverse Event
- CI Chief Investigator overall
- CRF Case Report Form
- DMC Data Monitoring Committee
- GCP Good Clinical Practice
- ICF Informed Consent Form
- NHS National Health Service
- P/GIS Parent / Guardian Information Sheet
- PI Principal Investigator at a local centre
- PIS Participant Information Sheet
- REC Research Ethics Committee
- R&D Research and Development department
- SAE Serious Adverse Event

FUNDING AND SUPPORT IN KIND

FUNDER(S) (Names and contact details of ALL organisations providing funding and/or support in kind for this study)	FINANCIAL AND NON FINANCIALSUPPORT GIVEN
National Institute for Health Research Research For Patient Benefit	Full funding for this study

ROLE OF STUDY SPONSOR AND FUNDER

Nottingham University Hospitals NHS Trust are the sponsor for this study. This study is funded by the National Institute for Health Research (NIHR) Research For Patient Benefit (project reference NIHR200580). The views expressed are those of the author(s) and not necessarily those of the NIHR or the Department of Health and Social Care.

The study sponsor will monitor the study conduct against nationally agreed standards. The study sponsor and study funder will have no role in the design, data analysis, interpretation, manuscript writing and dissemination of the results. The sponsor and funders will be consulted for the final decision/s regarding any aspects of this study. The Sponsor reserves the right to discontinue this trial at any time for failure to meet expected enrolment goals, for safety or any other administrative reasons. The Sponsor shall take advice from the Trial Steering Committee and Data Monitoring Committee as appropriate in making this decision.

ROLES AND RESPONSIBILITIES OF STUDY MANAGEMENT COMMITTEES/GROUPS & INDIVIDUALS

Study Steering Groups

The Chief Investigator has overall responsibility for the study and shall oversee all study management. The Chief Investigator will provide supervision for students involved in the research.

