3.3. COMPLIANCE

Study compliance is one of the primary objectives to be measured as part of the feasibility trial. The study will quantify:

- 1. Self-reported treatment compliance: patient diaries will be completed with an option to complete usage time, in hours, of the treatment device. This diary will be returned for analysis at the two week follow up visit
- 2. Outcomes compliance: completion of outcome tools will be monitored with an expected completion of instrument items of 95%. Patients will be provided with a reminder to complete outcomes and provided with options for returning the 12 week follow up as electronic, postal or by telephone
- 3. Clinic attendance: clinic attendance will be monitored particularly the completion of 6 week follow up outcomes assessment.

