4.3. RANDOMIZATION AND BLINDING

Participants will be individually allocated in a 1:1:1 ratio to one of the three treatment groups using a minimisation algorithm by the Nottingham Clinical Database Support Service (CDSS) and held on a secure server. The minimisation variables will comprise age, injury type and study site. The investigator or authorised designee will use the remote, internet-based randomisation system to obtain the treatment allocation for each participant. Other than the allocated treatment, all groups will be followed up in the same way to exclude bias.

It will not be possible to blind participants to treatment allocation. Assessor blinding will be achieved by removal of the treatment device by nursing staff independent to the trial on arrival to follow up clinic for those children who require an appointment to remove a cast. Follow up will be performed remotely by the central trial team. Non-response will be minimised through the use of electronic and telephone reminders.

Maintenance of randomisation codes and procedures for breaking code

Access to the randomisation system will be confined to the CDSS IT staff.

In most cases, the un-blinding will be part of managing an SAE, and will be reported with the SAE, however, in cases where un-blinding was not associated with an SAE, such actions should be reported in a timely manner. The default will be to use the same timeline requirements for investigator reporting of SAEs (notification of Sponsor immediately as practicable by phone or email, followed by a written narrative of the event within 48 hours).

No interim analysis is planned during this study. At the end of the study, anonymous linked records of outcomes and treatment allocation will be provided for analysis.

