5.1. STUDY ACTIVITIES FOR THE TRIAL

At time of diagnosis (typically in the Emergency Department), potential participants may be identified and provided with a patient information sheet by the usual care team. Screening of participants may also be performed by the usual care team in face-to-face or virtual fracture clinics and information sheets provided.

CONFIDENTIAL ANCHOR Trial Protocol v3.2 28.02.22 IRAS ID 277534 page 19 of 33
FUNDED BY
NIHR National Institute
for Health Research

Where eligible participants wish to join the study, a member of the research team will obtain informed consent and undertake randomisation to a product at the point in the local care pathway where a definitive treatment is being offered. This may be in the Emergency Department, Emergency clinics or fracture clinic depending on the local pathways.

Following completion of pre-injury baseline scores and CRF, the patient will be randomised using a web-based electronic randomisation with 1:1:1 allocation with stratification for fracture type (occult and visible fracture line) and child age (5-10, 11-15) with block sizes of 3, 6 & 9.

Treatment will be provided according to random allocation by a trained member of the clinic staff according to the manufacturer's guidelines. As described in section 4.2, the available treatments are:

- 1. Supportive bandage.
- 2. Semi-rigid, removable brace (including splints or custom orthoses).
- 3. Below knee walking cast

Routine follow up will be provided according to local protocols and decided by the usual care team. Patients who have a below knee walking cast are likely to require a clinic review to remove the device. Other patients may be discharged with instructions to remove their own device at home.

A patient diary is provided to participants at time treatment is provided. The diary is returned after two weeks.

Outcome assessment will be completed by the central research team using an electronic interface through the Redcap system. Outcomes will be collected at 2 weeks, 6 weeks and 12 weeks. Telephone, SMS text messages (Esendex, Nottingham) and e-mail reminders will be used to encourage completion of outcome scores.

	Baseline (pre- injury) score	Review 1 (Day 7-23)	Review 2 (Day 35-52)	Review 3 (Day 84-100)
Demographics	Х			
Physical function (PROMIS Mobility)	х	х	Х	Х
Quality of life (EQ-5D-Y)	х	Х	х	Х
Daily pain (faces pain or VAS)	х	Х		
Re-injuries			Х	Х
Complications		Х	Х	Х
Parent satisfaction			Х	Х
Child satisfaction			Х	Х

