7.8. Adverse Event

Potential adverse events

Table 4 lists adverse events reported in previous trials of childhood low-risk ankle fractures.

Children participating in the ANCHOR Trial will be screened at clinical follow up for the following potential adverse events:

- Pressure related issues
 - o Heel pain
 - o Blisters
 - o Sores
- Skin irritation or rashes
- Persistent swelling
- Persistent bruising
- Additional visits to healthcare providers (e.g. physiotherapy, fracture clinic etc)

Table 4 Adverse events reported in previous trials of "low-risk" ankle fractures

Trial	Adverse events	
Boutis et al 2007[18]¤	Unscheduled visits to healthcare provider	
	Skin irritation / rash	
Barnett et al 2012[19]	Additional visits to healthcare provider	
	Pressure related complications	
Gleeson et al 1996[16]	No adverse events reported	
Launay et al 2008[17]	Persistent swelling and bruising	

Reporting Procedures

Proportionate to the type of study and participant involvement, all adverse events should be reported. Depending on the nature of the event the reporting procedures below should be followed. Any questions concerning adverse event reporting should be directed to the Chief Investigator in the first instance.

Non serious AEs

All such events, whether expected or not, should be recorded.

Serious AEs

An SAE form should be completed and sent to the Chief Investigator within 24 hours. Hospitalisations for elective treatment of a pre-existing condition do not need reporting as SAEs.

All SAEs should be reported to the Derby REC where in the opinion of the Chief Investigator, the event was:

'related', ie resulted from the administration of any of the research procedures; and

'unexpected', ie an event that is not listed in the protocol as an expected occurrence

Reports of related and unexpected SAEs should be submitted within 15 days of the Chief Investigator becoming aware of the event, using the NUH SAE form for non-CTIMP studies.

Local investigators should report any SAEs as required by their Local Research Ethics Committee and/or Research & Development Office.

The Sponsor Contact Details for SAEs are:

- Email ([contact])
- Hand delivered not mailed ([name])
- [contact]) if written report not immediately possible

Any queries please contact a member of staff in the Nottingham University Hospitals Research & Innovations department:

- [contact]
- Email: [contact]

Participant removal from the study due to adverse events

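### Follow-up is described as the same in all arms, but the cast arm has an extra clinic route for adverse-event screening and diary return, and the assessor-blinding statement claims more than is masked

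*Protocol*

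**What the plan says.** **Follow-up.** Section 4.3 of the protocol states "Other than the allocated treatment, all groups will be followed up in the same way to exclude bias", and adds that the central trial team performs follow-up remotely. Section 5.1 has that team collect outcomes through REDCap at 2, 6 and 12 weeks. Table 3 in the same section marks complications at Reviews 1, 2 and 3, with no distinction by arm.

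**Clinic attendance.** Section 5.1 leaves routine follow-up to local protocols and the usual care team. It then separates the arms: "Patients who have a below knee walking cast are likely to require a clinic review to remove the device", whereas "Other patients may be discharged with instructions to remove their own device at home".

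**Adverse events.** Section 7.8 says "Children participating in the ANCHOR Trial will be screened at clinical follow up for the following potential adverse events". The list covers pressure problems, skin irritation, persistent swelling and bruising, and "Additional visits to healthcare providers (e.g. physiotherapy, fracture clinic etc".

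**Diary.** Section 3.3 says "This diary will be returned for analysis at the two week follow up visit". Section 5.1 says that it comes back after two weeks and names no route. Under section 3.2 the diary is the source for adherence and daily pain.

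**Blinding.** The Study Summary states "Assessors blinded but participants cannot be blinded". The step described in section 4.3 is removal of the device by nursing staff independent of the trial, "on arrival to follow up clinic for those children who require an appointment to remove a cast".

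**The concern.** Read together, sections 5.1 and 7.8 mean that a face-to-face look for the listed events is likely for a cast child and may never happen for a bandage or brace child. Sections 3.3 and 5.1 do the same for handing in the diary. An arm that is looked at more closely tends to show more events and to return more diaries, whatever the treatments do.

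Two results depend on this. Progression criterion 2 (section 3.4) asks whether any intervention has an unacceptable complication rate. Section 3.3 makes compliance a primary objective. Section 4.2 also reports that pressure injuries are more common with a removable brace than with a cast, so the arm where that harm is expected is one that may miss the clinic screen.

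The blinding statement raises a related problem. A reader of the Study Summary would credit the outcomes with masked assessment, but the step described concerns one group of attenders at a clinic, while the outcomes are collected remotely.

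**Working it through.** The protocol gives no figure on this point, so the main check sets the sections side by side.

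| Item | Remote wording, all arms | Clinic wording |
|---|---|---|
| Outcome follow-up | 4.3 and 5.1: central team, REDCap, 2, 6 and 12 weeks | Appendix 2: only the 12-week contact is marked online; 3.3 monitors clinic attendance, particularly for the 6-week assessment |
| Complications | Table 3: Reviews 1 to 3 | 7.8: itemised screen at clinical follow-up |
| Diary | 5.1: returned after two weeks, no route | 3.3: at the two-week visit; Appendix 2: collected at 2 weeks |
| Device removal | 5.1: non-cast children may do this at home | 5.1: cast children likely to attend; Appendix 2: listed at 2 weeks for all |

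1. If follow-up is remote, as 4.3 and 5.1 say, the clinic screen in 7.8 and the hand-in in 3.3 reach mainly the cast arm.
2. If every child attends at 2 and 6 weeks, as Appendix 2 and 3.3 suggest, the routes are equal, but 4.3 and 5.1 are then wrong.
3. The sections do not settle which applies, so equal ascertainment is not assured by the text.

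**Illustration only; every rate is assumed.** Let *p* be the true event risk, equal in all arms. Let 90% of cast children and a share *v* of 10% to 30% of the others attend clinic. Detection is 95% with a clinic visit and *s*, from 30% to 80%, without one.

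- Observed cast rate = *p* × (0.90 × 0.95 + 0.10 × *s*)
- Observed other rate = *p* × (*v* × 0.95 + (1 − *v*) × *s*)

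Mild case, *s* = 0.80 and *v* = 0.30:
- cast: *p* × (0.855 + 0.080) = 0.935*p*
- other: *p* × (0.285 + 0.560) = 0.845*p*
- ratio: 0.935 / 0.845 = 1.11

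Strong case, *s* = 0.30 and *v* = 0.10:
- cast: *p* × (0.855 + 0.030) = 0.885*p*
- other: *p* × (0.095 + 0.270) = 0.365*p*
- ratio: 0.885 / 0.365 = 2.42

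With *p* = 10% and the 42 per arm of section 6.2, the expected counts are 3.9 against 3.5 (mild) and 3.7 against 1.5 (strong). If remote detection equals clinic detection (*s* = 0.95), both multipliers are 0.95 and the ratio is 1.0.

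If only the common remote source is counted, both arms have rate *p* × *s*, and the ratio is 1.0 for any *s*, provided families in all arms report equally well.

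**Blinding.** Taking the device off before a clinic assessment can mask a clinic assessor. It masks nothing when follow-up is remote, and the step is written only for cast-removal attenders. Global rating of change, satisfaction and pain are the family's own judgement, and section 4.3 accepts that participants know their allocation.

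**The case against.** The best defence is that trial follow-up and routine care are different things. Section 4.3 excepts the allocated treatment, cast removal belongs to that treatment, and the central follow-up is the same in every arm. Complications are a listed outcome collected at all three reviews, so criterion 2 already has a common source, and the case report form, which is not shown, may already carry the 7.8 items. This largely stands. A reader might infer that safety data are collected by wholly different means in each arm; Table 3 does not support that. What remains is the extra clinic route, and nothing says which source criterion 2 uses.

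A reader might also infer that every planned cast-removal visit counts as an adverse event, giving up to 42 of 42 in the cast arm. The text does not support this: the listed item is an *additional* visit, and Appendix 2 schedules device removal. A one-line definition is enough.

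On the diary, section 5.1 requires no clinic visit, and section 4.4 reports missing data by arm, so an imbalance would be visible. That is fair, but section 4.4 also rules out imputation and adjustment, so the imbalance would be seen and not corrected.

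On blinding, a reader might conclude that nobody is masked, or that attending clinic reveals the arm. Both go too far. Section 4.3 confines randomisation-system access to the database service's IT staff and supplies linked allocation records for analysis at the end of the study, and other children may also attend clinic. The protocol is open about unblinded participants. It does not state, however, that the central team collecting outcomes is unaware of allocation.

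**Conclusion.** The point holds as an unreconciled conflict between clinic-based and remote wording, with a consequence for ascertainment. As written, the cast arm has a common remote source plus a likely face-to-face screen and diary hand-in; the other arms have the remote source and perhaps a visit. Complication rates under criterion 2, and diary-based adherence and pain, may therefore be ascertained unequally.

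The size cannot be derived from the protocol. The range of 1.1 to 2.4 rests entirely on assumed attendance and detection, and the ratio is 1.0 if the remote reviews detect as well as the clinic. Counts are small in any case: one event in 42 is 2.4 percentage points (1/42), and criterion 2 is a steering-committee judgement with no stated threshold.

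The assessor-blinding statement is broader than the step that supports it. It should be narrowed rather than removed. No sample size changes.

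**What to change.** - Reconcile sections 3.3, 4.3, 5.1, 7.8 and Appendix 2 on which contacts are remote and which are visits.
- Ask the 7.8 items in the remote Reviews 1 to 3 in all arms, and base progression criterion 2 on that common source. List events found only in clinic separately, by source, so that none is lost from safety reporting.
- Use one diary-return route, electronic or postal, in all arms.
- State that planned device removal is not an additional healthcare visit.
- Limit the assessor-blinding statement to the steps that are actually masked, say whether the central team is kept unaware of allocation, and state that the participant-reported outcomes come from unblinded families.

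The cost is a few added REDCap items, changes of wording, and a less favourable description of blinding. Remote questions may miss some signs that an examination would find, but the same source would then be used in every arm. No extra visits are needed.

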4.4. STATISTICS

Feasibility outcomes

All analyses will be documented in a Statistical Analysis Plan which will be finalised prior to database lock. Descriptive statistics (with 95% confidence intervals (CI) where appropriate) will address feasibility objectives (e.g. recruitment and follow-up rates, missing clinical outcome data, intervention adherence, standard deviations for clinical outcomes). Demographic and baseline clinical characteristics will be descriptively compared by study arm.

Assessment of efficacy

As this is a feasibility study, no formal assessment of efficacy will be undertaken. The potential primary clinical outcome for the future main trial will be analysed descriptively per arm, with confidence intervals generated using appropriate regression model to estimate the likely range of intervention effects. Secondary clinical outcomes will be descriptively summarised by treatment arm.

There is no consensus yet on the outcomes that should be measured in childhood fractures. In our preparatory work for this proposal families have identified 'return to normal activities' and 'pain' as the two most important outcomes.

Initial findings from the CORE-KIDS lower limb fracture study have suggested that the EQ-5D-Y and PROMIS Mobility outcome sets should be used as the primary outcome measures, as they assess a broad range of function and mobility domains.

A formal minimally important clinical difference (MCID) in this patient group has not been calculated, and previous trialists have used a range between 5 and 7%^{9,10} to represent an important difference.

Assessment of safety

No significant safety issues are expected related to this trial. Spontaneous adverse events will be monitored during the trial, in particular at the 6-week follow up requiring additional treatment or physiotherapy.

All adverse events will be discussed at the trial management group meetings. Significant adverse events will be escalated to the trial steering committee and study sponsor.

Procedures for missing, unused and spurious data

Proportions and patterns of missing data will be summarised by arm but there will be no imputation for missing data at follow-up assessments nor any model-based adjustment for missing data.

Baseline and outcome data will be summarised by allocated group, regardless of adherence with the intervention. Safety will be evaluated using the Safety set: All randomised participants who receive at least one treatment.

4.5. QUALITATIVE ANALYSIS

A qualitative evaluation of interview transcripts will be performed to identify themes in

- 1. Treatment compliance
- 2. Attitudes to randomisation
- 3. Treatment experience

Interviews will be transcribed and anonymised. A framework analysis will be performed based on the SWIFFT analytic framework[23]. Initial coding of data will be led by one researcher. Verification of lower-level coding will be performed by the senior qualitative researcher with any disagreements resolved by consensus. Higher level themes and, if required, revision of the framework will be discussed and agreed by the trial steering committee.

5. STUDY SETTING

This is a multi-centre trial. The setting for this study will be hospitals that provide care for children aged 5-15 with low-risk ankle fractures or clinically undisplaced ankle fractures. The design of this study is to minimise the additional research burden on participants and NHS teams.

5.1. STUDY ACTIVITIES FOR THE TRIAL

At time of diagnosis (typically in the Emergency Department), potential participants may be identified and provided with a patient information sheet by the usual care team. Screening of participants may also be performed by the usual care team in face-to-face or virtual fracture clinics and information sheets provided.

CONFIDENTIAL ANCHOR Trial Protocol v3.2 28.02.22 IRAS ID 277534 page 19 of 33
FUNDED BY
NIHR National Institute
for Health Research

Where eligible participants wish to join the study, a member of the research team will obtain informed consent and undertake randomisation to a product at the point in the local care pathway where a definitive treatment is being offered. This may be in the Emergency Department, Emergency clinics or fracture clinic depending on the local pathways.

Following completion of pre-injury baseline scores and CRF, the patient will be randomised using a web-based electronic randomisation with 1:1:1 allocation with stratification for fracture type (occult and visible fracture line) and child age (5-10, 11-15) with block sizes of 3, 6 & 9.

Treatment will be provided according to random allocation by a trained member of the clinic staff according to the manufacturer's guidelines. As described in section 4.2, the available treatments are:

- 1. Supportive bandage.
- 2. Semi-rigid, removable brace (including splints or custom orthoses).
- 3. Below knee walking cast

Routine follow up will be provided according to local protocols and decided by the usual care team. Patients who have a below knee walking cast are likely to require a clinic review to remove the device. Other patients may be discharged with instructions to remove their own device at home.

A patient diary is provided to participants at time treatment is provided. The diary is returned after two weeks.

Outcome assessment will be completed by the central research team using an electronic interface through the Redcap system. Outcomes will be collected at 2 weeks, 6 weeks and 12 weeks. Telephone, SMS text messages (Esendex, Nottingham) and e-mail reminders will be used to encourage completion of outcome scores.

	Baseline (pre- injury) score	Review 1 (Day 7-23)	Review 2 (Day 35-52)	Review 3 (Day 84-100)
Demographics	Х			
Physical function (PROMIS Mobility)	х	х	Х	Х
Quality of life (EQ-5D-Y)	х	Х	х	Х
Daily pain (faces pain or VAS)	х	Х		
Re-injuries			Х	Х
Complications		Х	Х	Х
Parent satisfaction			Х	Х
Child satisfaction			Х	Х
GROC		Х	Х	Х

Table 3 Schedule of outcome assessment. Demographic included: age; gender; side of injury; mechanism of injury; dominant side; location of injury; type of fracture. GROC: Global rating of change score

Study activities for interviews

A subgroup of participants recruited to the ANCHOR trial will be invited to complete structured interviews regarding the study experience. 4-6 participant dyads who declined to be randomised to the

trial will also be recruited. A target of 24 parent-child dyads will be interviewed after the 12-week follow up and before 24 weeks have elapsed since randomisation.

Purposeful sampling will be undertaken to conduct interviews with a balance of families:

- From different recruiting sites
- With different treatments
- With different ages of child (5-10, 11-15)

As advocated in the child health literature, a pragmatic and participant-centred approach (based on choice, participation, and flexibility) to collecting qualitative data will be employed[24]. Interviews will be conducted with children and parents/legal guardians either collectively or separately. Interviews will take place at the participants' preferred time and method (e.g. face-to-face, telephone)[24]. This interview will follow a standard interview schedule including questions for both the person with parental responsibility and children. This schedule will be piloted with our PPI group to confirm acceptability and validity of the tool.

The interviews will explore the experience of participation in a trial, acceptability of treatments, barriers to participation and adherence to the study protocols and strategies to promote recruitment and retention to a future full trial.

It is anticipated that most interviews will be performed by members of the research team working at the lead site (Nottingham University Hospitals NHS Trust). However, members of local research teams with adequate qualitative research experience (as judged by the Chief Investigator and as indicated on the delegation log) may also perform interviews using the standard interview schedule. Audio files will be transferred to the lead site using secure NHS email servers.

